3.8 Selection criteria

The **inclusion criteria** for this study is as follows:

- ✚ A self-reported BQ chewer who has been chewing BQ for the past 6 months with atleast 2-3 chewing episode per week. The ingredient of BQ must include AN without or without smokeless tobacco.
- ✚ Other optional ingredients such as slaked lime and betel leaf are allowed.
- ✚ Age of participant must be 18 year old or above
- ✚ Participants must be residing in study location (Kota Belud, Sabah)
- ✚ Ability to comprehend, converse and read in Bahasa Melayu and their local language (Bajau)
- ✚ Participants who are able to provide written consent and agree to comply with all protocol-specified procedures such as providing saliva samples, participating in five 1-2 hours sessions of intervention over 22 days and agree to attend follow-up sessions on first and third month

The **exclusion criteria** for this study are as below:

- ✚ Non-Malaysian citizen
- ✚ Participants who are not willing to quit the BQ chewing habit at the time of the study
- ✚ Women who are pregnant or nursing at the time of study
- ✚ Individuals with psychiatric illness or special social situations that would limit their compliance with study requirements

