3.10.1.1 Baseline & Follow- up Questionnaire

A structured questionnaire (Appendix C) will be used in this study. The questionnaire will be adapted from the BENIT trial (Paulino YC et al., 2020). In the **baseline survey**, questions regarding demographics, BQ chewing behaviours, BQ composition, BQ dependency level, reasons for chewing, readiness and self-perceived barriers to quit will be asked.

On the 22-day, 1-month and 3-month, a follow-up questionnaire will be prepared. Information consisting of intervention compliance (whether they had attempted to quit chewing since start of the intervention), current chewing status (current chewer or ex-chewer), how much the participants had cut down on their chewing (quids/day), how many group sessions the participants attended (as well as reasons for absent if missed any sessions) and BQ composition if the participants are still chewing.

Several composite questions from other validated questionnaire will be added to existing questionnaire set to achieve a strategic fit to meet the objective of this study; BQ composition (Tahir Z & Doss JG, 2003), BQ dependency level (Herzog TA et al., 2014), reason for chewing (Little MA et al., 2014), readiness and self perceived barriers in ceasing the habit (Maling TH, 2016 & Brown RA, 2003).

Prior to formulation and adaptation of the questionnaire, permission to use and modify the established questionnaire will be obtained from original author (Paulino YC et al., 2020).

Below are the summaries,

The baseline questionnaire (Appendix C) will be comprised of:

- a) Section A – to obtain demographics information of the study participants
- b) Section B – to assess the BQ chewing behaviours (including chewing history)
- c) Section C – to assess BQ composition used by the participants
- d) Section D – to assess the BQ dependency level
- e) Section E – to assess the reason for betel quid chewing
- f) Section F – to assess the readiness and self perceived barriers to quit habit

The follow up questionnaire (Appendix M) (22-day, 1-month & 3-month) :

- a) Section A – brief personal particulars of the participants
- b) Section B – to assess participant’s compliance towards the intervention by assessing the total number of session attended and reasons if absent
- c) Section C – to assess the current chewing status
- d) Section D – to assess number of cut-down of habits by the participants (quid/day)
- e) Section E – to assess BQ composition (if still chewing)

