3.10.3.2 Implementation of the Study

Control Group

The community screening program for the control group will be organised at the community hall. Villagers who attended the screening program will first be registered and screened for eligibility to participate in the study (**Checkpoint 1**). The eligible participants will be briefed on the nature of the intervention and will be invited to participate. A copy of 'Patient Information Sheet' (PIS) (Appendix A) will be explained and given for reference about the study details and written informed consents (Appendix B) will be obtained from the villagers prior admitting them into the study.

Only consented participants will be interviewed by the trained interviewers (**Checkpoint 2**). Information regarding demographics details and baseline information of BQ chewing behaviours, BQ composition, BQ dependency levels, reasons for chewing, readiness and self-perceived barriers to quit will be obtained. No intra-oral clinical examination will be carried out in this study.

Upon completing of the interview, participants will be given an educational booklet which contains general information regarding AN and BQ, risk associated with BQ chewing behaviour, cessation strategies that are modeled after tobacco cessation and researcher's contact information. After an one-to one explanation about the educational booklet to the participants by the interviewer, they will be ushered to saliva collection counter (**Checkpoint 3**) to provide their baseline saliva sample. Participants will be thanked and given a token of appreciation before they are ushered out of the community hall.

Participants will be provided with an appointment card to return on the 22-day, 1-month and 3-month for follow-up. Follow-up questionnaire and saliva samples will be taken on 22-day and 3-month, whereas a community perception analysis will be performed at 1-

month together with completion of follow-up questionnaire. The summary of participant's flow for the control group is illustrated in Figure 3.6.

[figure not shown]

Figure 3.6 Summary of Participant's Flow for the Control Group in this study

Intervention group

Screening (Day 0)

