The community screening program for the intervention group will be organised at the community hall on a Saturday. Villagers who attend the screening program will first be registered and screened for eligibility to participate in the study (**Checkpoint 1**). The eligible participants will be briefed on the nature of the intervention and will be invited to participate. A copy of 'Patient Information Sheet' (PIS) (Appendix A) will be given for the reference about the study details and written informed consents (Appendix B) will be obtained from the villagers prior admitting them into the study.

Only consented participants will be interviewed by the trained interviewers (**Checkpoint 2**). Face-to-face interviews will be carried out to gain participant's information regarding demographics details and baseline information of BQ chewing behaviours, BQ composition, BQ dependency levels, reasons for chewing, readiness and self-perceived barriers to quit habit. No intra-oral clinical examination will be carried out in this study.

Upon completion of the interview, participants will be briefly explained and given an educational booklet which contains general information regarding AN and BQ, risk associated with BQ chewing behaviour, cessation strategies that are modeled after tobacco cessation and researcher's contact information. They will then be ushered to saliva collection counter (**Checkpoint 3**) to provide their baseline saliva sample.

Participants will be thanked and given a token of appreciation before being ushered out of the community hall and will be reminded to return the next day (Sunday) to initiate the first support session for the cessation intervention. For every intervention session attended by the participants, they will be monetarily incentivized for their time and commitment for cessation. Appointment card will be provided to ease participants reference of support session dates.

A self explanatory video presentation regarding general information of AN and BQ, the ill health effects of BQ and introduction and importance of cessation program will be continuously played **for the non- chewers in the village hall** to increase their knowledge and awareness while they are waiting for their family members. who are undergoing the screening. This can help maximise their support for their loved ones who are trying to quit the risk habit.

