Checkpoint 3 will be prepared for completion practice of Social Support for Non-BQ Chewing Worksheet (Appendix K). It is a tool to maximise the social support of the participant to quit the behaviour. Social support can be a good source of motivation and may also act as a buffer for stressful situations. Thus, they play a positive role in the success of participants in remaining abstinent. Thus, in this checkpoint, the participants will be guided to identify their social support and record behaviours of others that are helpful and not helpful in their non-chewing efforts, and also activities that the participants would like others to increase or decrease to help them in their journey of quitting chewing. Facilitators will personally guide the participants to complete this worksheet to give them a headstart.

[figure not shown]

Figure 3.10 Summary of Participants' Flow on the 3rd Session of the Intervention (Day 15)

4th Session (Day 18)

On the **4th session of the intervention (Day 18)**, participants will be registered at Checkpoint 1. Discussion on the overall quitting experience of the participants will be held in the hall on how participants coped with triggers, the challenges in the high risk situations and the benefits they gained from the 3 days of quitting experience will be highlighted during the discussion. The arecoline fading worksheet will be collected and reviewed and discussed with participants. The facilitators will further emphasize the negative health effects of BQ chewing and accentuate the oral cancer risk that is contributed by BQ chewing behaviour. Additional coping strategies will be discussed to address newer urges to chew. Reinforcement will be given for both quitters and current chewers through a talk by the main researcher.

[figure not shown]

Figure 3.11 Summary of Participants' Flow on the 4th Session of the Intervention (Day 18)

5th Session (Day 22)

On the **5th session of the intervention (Day 22)**, participants will register their attendance at **Checkpoint 1** and will be required to complete a follow-up questionnaire. The questionnaire will enquire regarding brief personal particulars, patient's compliance, current chewing status, number of cut-down of habit by the participants (quid/day), total number of sessions attended and reasons if absent and the BQ composition if participants are still chewing.

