Later, a discussion on the overall quitting experience will ensue. Participants who have relapsed and started chewing but are willing to attempt to quit again will be encouraged. **Strategies for managing thoughts** that could lead to relapse will be introduced. The participant's lifestyle changes that supports quitting will be reviewed. Usage of "excuses" for not chewing and employing "fake chew" will be reinforced.

The **Positive and Negative Thoughts Worksheet (Appendix L)** will be a strategy to manage the thoughts that participants might have through their quitting journey. This method is based on the notion that mood is related to the balance of the positive and negative thoughts. When negative thoughts outweighed the positive thoughts, the result is a depressive, anxious, angry or other symptoms that precipitate the behaviour of risk habit such as chewing to overcome it (Brown RA et al. 2003). The thoughts with a clear message of positivity or negativity should be recorded and it is curcial to discern which type of thoughts dominates in this process. The negative thoughts can be managed with the coping skills that they were thought before. The main researcher will brief all participants regarding this thought management through a talk.

Checkpoint 2 will be prepared for completion practice for Positive and Negative Thoughts worksheet (Appendix L). One of their current positive and negative thoughts will be used as a practice. At the end of session 5, **Checkpoint 3** will be prepared as saliva collection counter for participants to provide their 22-day saliva samples.

[figure not shown]

Figure 3.12 Summary of Participants' Flow on the 5th Session of the Intervention (Day 22)

3-month follow up (Day 90)

On **3- Month follow up**, participants will be assessed of their chewing abstinence through a follow up questionnaire after registration (**Checkpoint 1**). The items that will be required are brief personal particulars, participant's current chewing status, number of cut-down of habit by the participants (quid/day) and BQ composition if participants are still chewing. All participants will be motivated and encouraged regardless their success in quitting the BQ behaviour. A repeated educational talk of adverse effects of AN and BQ chewing habit will be given. A summary of community perception will be informed to the participants and they will be encouraged to contact research team if they needed any form of help in cessation in the future.

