3.12 Outcome of the Study

3.12.1 Primary Outcome Measures

Change in the number of participants who self-reported that they had quit BQ chewing will be measured through follow-up questionnaire at day 22. This will represent the short-term cessation prevalence achieved by the study.

Change in the number of participants who self-reported that they had quit BQ chewing will be measured through follow-up questionnaire at Month-3. This will represent the intermediate-term cessation prevalence (stay-quit) achieved by the study.

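### Intervention-arm Day 22 questionnaire and saliva are described only as parts of treatment Session 5, so assessment depends on treatment attendance in one arm only

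*Protocol*

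**What the plan says.** Protocol 3.12.1 makes Day 22 self-reported quitting a primary outcome, which "will be measured through follow-up questionnaire at day 22". Section 3.12.2 makes the Day 22 salivary biomarkers a secondary outcome.

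**Intervention arm (3.10.3.2).** At Session 5 participants register at Checkpoint 1 "and will be required to complete a follow-up questionnaire". After the discussion, talk and worksheet, Checkpoint 3 "will be prepared as saliva collection counter for participants to provide their 22-day saliva samples". Table 3.4 lists the follow-up questionnaire under Session 5. On the card given at screening: "Appointment card will be provided to ease participants reference of support session dates".

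**Control arm (3.10.3.2).** "Participants will be provided with an appointment card to return on the 22-day, 1-month and 3-month for follow-up". This arm has no treatment sessions.

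**Both arms.** The eligibility criterion in 3.8 asks for agreement to "participating in five 1-2 hours sessions of intervention over 22 days and agree to attend follow-up sessions on first and third month". It names no Day 22 assessment apart from the sessions. Section 3.14.2 describes the Day 22 interview and saliva in general terms, without a venue and without a procedure for people who do not come.

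**The concern.** Session 5 falls one week after quit day and centres on the experience of quitting and on relapse. A participant who never quit, or who has relapsed, has an evident reason to stay away, and as described loses the Day 22 assessment along with the session. A control who is still chewing is asked back only for an interview and a sample.

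If absence goes with continued chewing, chewers drop out of the assessed group in the intervention arm through a mechanism that controls do not share. Day 22 cessation among those assessed would then favour the intervention for a reason unrelated to its effect. This is a matter of how data are collected: an analysis plan can decide how to treat a missing interview, but it cannot recover a saliva sample that was never taken.

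**Working it through.** **1. Is there another route to a Day 22 assessment?** Places that could supply one:

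- 3.1: the same participants are to be followed up at Day 22 and 3 months. This states the intent, not a procedure.
- 2.12: participants who relapse are to be encouraged and brought back into the intervention. This returns them to treatment. It is not an assessment.
- 3.9: a participant may withdraw from some components only. Leaving the sessions while staying in follow-up is therefore allowed, but how such a person is assessed on Day 22 is not said.
- 3.14.2: face-to-face interview and saliva. No home visit, call, catch-up or assessment-only attendance.
- 3.10.3.2: the only operational description, and it lies inside Session 5.

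None gives a route. Figures 3.1 and 3.12 are not shown in the text available, so they could not be checked.

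**2. Inputs for the size.** All from 3.4: quit rates 38.64% (intervention) and 9.09% (control), 46 per arm after a 20% dropout allowance. The plan's own figures reproduce. A two-sided 5% test with 80% power and continuity correction gives 38 per arm (76 in total), and 76 × 1.2 = 91.2, rounded up to 46 per arm (92). The share missing Session 5 is not in the documents. I assume 10% and 20%, the latter equal to the dropout allowance.

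**3. Inflation among those assessed.** Let P be the true quit rate in the arm, m the share absent and r the quit rate among absentees:

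observed rate = (P − m·r) / (1 − m)

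With P = 38.64%:

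| m | r = P (absence unrelated to chewing) | r = P/2 = 19.32% | r = 0 (all absentees chew) |
|---|---|---|---|
| 10% | 38.6% | (38.64 − 1.93)/0.9 = 40.8% | 38.64/0.9 = 42.9% |
| 20% | 38.6% | (38.64 − 3.86)/0.8 = 43.5% | 38.64/0.8 = 48.3% |

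In counts, for the bottom right cell: 46 × 0.3864 = 17.8 quitters, 46 × 0.8 = 36.8 assessed, 17.8/36.8 = 48.3%. The bias runs from 0 to +9.7 points at 20% absence and from 0 to +4.3 points at 10%.

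**4. Effect on the test when there is no true difference.** Take 36.8 assessed per arm, intervention absentees all chewing and control losses unrelated to chewing. The nominal two-sided 5% test then rejects about 6.2% of the time at a common quit rate of 9.09%, 8.0% at 20% and 13.2% at 38.64%. These use a normal approximation and ignore clustering by village.

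**5. Counting absentees as chewers.** This gives (1 − m) × observed rate = P − m·r. With r = 0 it returns 17.8/46 = 38.64%, with no bias. With r = P/2 and m = 20% it gives 38.64 − 3.86 = 34.8%, an error in the other direction. It yields no biomarker levels in either case.

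**The case against.** **Inference from silence.** A reader might infer that anyone who leaves the sessions definitely has no Day 22 outcome. The documents do not say that. Nothing makes assessment conditional on treatment, 3.1 intends follow-up of everyone, and someone who missed earlier sessions but comes on Day 22 is assessed. This stands: the finding is that no route is described, not that one is forbidden.

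**An analysis could repair it.** A reader might infer that no analysis of everyone enrolled can help. Step 5 shows otherwise for self-report. What remains is that the repair rests on an assumption and does nothing for saliva.

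**The size is one-sided.** Controls who do not return are also unassessed, and relapsed controls may stay away too. If all absentees chew in both arms, the same factor 1/(1 − m) applies to each, and with no true effect no difference is created. Attendance is paid in 3.10.3.2, and facilitators are told to be non-judgmental. This stands, so the figures are an upper bound and not a forecast. Payment may reduce absence, but it rewards attending the session and the assessment together.

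**The restriction in 3.15.2 is the operative problem.** That section limits the cessation analysis to participants who attended all sessions, so a Session 5 absentee would be left out even if interviewed. This is correct, and the fix must cover it. Deleting that restriction alone would still leave no described way to obtain the absentees' Day 22 data.

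**Compliance data.** A reader might infer that the item on "how many group sessions the participants attended (as well as reasons for absent if missed any sessions" fails too, because the people with most absences are never asked and Session 5 cannot be counted. The documents do not support this. Section 3.10.1.1 places the item in the 22-day, 1-month and 3-month questionnaire, and Appendix M carries it, although the item lists for later visits in 3.10.3.2 (3-month) and 3.14.3 omit it. Attendance is registered before the Day 22 form is completed.

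**The appointment cards.** Day 22 is the date of Session 5, so a card of session dates already shows it. The cards illustrate the difference between the arms and add little beyond that.

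**Conclusion.** The point holds as a one-arm dependence of Day 22 ascertainment on treatment attendance, for a primary outcome and for the saliva samples meant to verify it. Its direction depends on absentees being more often still chewing, which is plausible but not shown. Its size depends on how many miss Session 5, which is unknown. With 10% or 20% absent, the upper bound is 42.9% or 48.3% against a planned 38.64%. That bound assumes all absentees chew and control losses are unrelated to chewing. If absence is unrelated to chewing, there is no bias.

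A reader might extend this to the trial's main hypothesis. The documents do not support that: section 1.7 sets it at 3 months, and 3.10.3.2 gives Month 3 its own follow-up visit in both arms. The change should be made because it is cheap and because Day 22 data that were not collected cannot be recovered afterwards.

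**What to change.** - In 3.10.3.2 and 3.14.2, state that every enrolled intervention participant is offered the Day 22 questionnaire and saliva collection, whether or not they attend Session 5 or attended earlier sessions, in the same hall, on the same day and with the same staff.
- State that people who do not come on Day 22 are followed up in the same way in both arms.
- In 3.15.2, remove the restriction to participants who attended all sessions from the Day 22 cessation analysis. Without this, the added assessments would not affect the reported rate.
- Take session counts from the Checkpoint 1 attendance registers.

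The cost is protocol wording and a few more interviews and saliva samples on Day 22.
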